## 10.2 ABBREVIATIONS

AE	Adverse Event
ADE	Adverse Device Effect
CFR	Code of Federal Regulations
CGI-I	Clinical Global Impression--Improvement
CMP	Clinical Monitoring Plan
CRF	Case Report Form
eCRF	Electronic Case Report Forms
FDA	Food and Drug Administration
FDAAA	Food and Drug Administration Amendments Act of 2007
FFR	Federal Financial Report
GCP	Good Clinical Practice
GMP	Good Manufacturing Practices
HIPAA	Health Insurance Portability and Accountability Act
ICH	International Conference on Harmonisation
IRB	Institutional Review Board
ISO	International Organization for Standardization
ITT	Intention-To-Treat
LSMEANS	Least-squares Means
MedDRA	Medical Dictionary for Regulatory Activities
MiniRQLQ	Mini Rhinoconjunctivitis Quality of Life Questionnaire
MOP	Manual of Procedures
NOSE	
PI	Principal Investigator
QA	Quality Assurance
QC	Quality Control
RQLQ	Rhinoconjunctivitis Quality of Life Questionnaire
rTNSS	Reflective Total Nasal Symptom Score
SAE	Serious Adverse Event
SADE	Serious Adverse Device Effect
SAP	Statistical Analysis Plan
SNOT-22	Sino-nasal Outcome Test
SOA	Schedule of Activities
SOP	Standard Operating Procedure
UADE	Unanticipated Adverse Device Effect
US	United States
UV	Unscheduled Visit
VAS	Visual Analog Scale
NRS	Numeric Rating Scale

12 APPENDIX I

PRO	Patient-reported outcome
rTNSS	Reflective Total Nasal Symptom Score
SAE	Serious adverse event
SAP	Statistical analysis plan
SAS®	Statistical analysis software
SD	Standard deviation
SNOT-22	22-Item Sino-Nasal Outcome Test
VAS	Visual analog scale

2 Introduction

This statistical analysis plan (SAP) contains the definitions of analysis sets, derived variables, and statistical methods for the analyses of efficacy and safety data from the study entitled, “*Feasibility Study of Multi-Treatment Posterior Nasal Nerve Modulation for Treatment of Chronic Rhinitis*”. This is a prospective, multicenter, open-label, feasibility study (Arrinex Clinical Investigational Protocol #CT-0005). Participants will be consented and enrolled before study procedures. All participants who receive treatment will be assessed through the 90-day follow-up.

3 Study Design

3.1 Study objectives

This study will evaluate the feasibility of treatment to the posterior nasal nerve at both the middle and inferior meatus locations within the nasal cavity. The primary objective is to evaluate the safety of treatment to the inferior meatus location. Secondary objectives are to evaluate the effectiveness and tolerability of treatment at the inferior meatus location.

3.1.1 Study Endpoints

The primary endpoint is the incidence of procedure-related serious adverse events (SAEs) and/or serious adverse device effects (SADEs)

Secondary endpoints are:

- Incidence of procedure-related adverse events (AEs) and/or adverse device effects (ADEs)
- Tolerability of treatment as rated by participant verbal report of pain/discomfort on the 11-point Numeric Pain Rating Scale (NPRS)
- Change from baseline in nasal symptoms using the reflective Total Nasal Symptom Score (rTNSS) at 30 and 90 days post treatment
- Change from baseline in nasal congestion and turbinate hypertrophy as assessed by nasal endoscopy 30 and 90 days post treatment

Additional exploratory analyses are:

- Procedural characteristics
- Physician evaluation of ease of treatment delivery using study device for inferior meatus location
- Change from baseline in patient-reported outcome (PRO) assessments at 30 and 90 days post treatment:
 - Nasal Obstruction Symptom Evaluation (NOSE)
 - Sino-Nasal Outcomes Test (SNOT-22)
 - Nasal symptom visual analog scale (VAS)
 - Mini Rhinoconjunctivitis Quality of Life Questionnaire (mini RQLQ)

- Physician assessment of participant change from baseline as measured by the Clinical Global Impressions – Improvement

All statistical analyses will be performed using SAS (version 9.4), unless otherwise noted.

3.1.2 Statistical hypothesis

As a feasibility study, there is not a formal hypothesis, power calculation, or sample size estimates for the primary endpoint.

Statistical analysis of the secondary efficacy (rTNSS) endpoint is based on the following hypothesis:

H_0 : Change from baseline = 0

H_a : Change from baseline \neq 0

3.1.3 Sample size calculation and assumptions

A convenience sample of 30 treated participants was determined to be adequate for the study.

4 General Analysis Definitions

4.1 Study start and duration of follow-up

A participant is considered enrolled at the baseline visit once all enrollment criteria were confirmed to be met. Patients not meeting the enrollment criteria are considered screen failures and were not enrolled.

All participants will receive bilateral cryoablation treatment with the ClariFix device in accordance with the Instructions for Use (IFU). Each side of the nasal cavity is to be treated at both the middle meatus and the inferior meatus. Each location received approximately 30 seconds of cryoablation treatment. A second 30-second treatment was permitted at each location at the physician's discretion.

All participants will attend the following postprocedure study visits (window):

- 7-Day in-office visit (\pm 3 days, AE and medication review only)
- 30-Day in-office visit (\pm 7 days)
- 90-Day in-office visit (\pm 14 days)

A listing of participants who discontinue before the 90-day visit will be provided in the clinical study report with the last visit completed and the reason for discontinuation. Possible reasons for early discontinuation include:

- Participant withdraws consent
- Participant is lost to follow-up
- Physician or sponsor withdraws participant for the health or welfare of the participant
- Participant death

4.2 Randomization

Not applicable.

4.3 Analysis sets

There are 2 analysis populations:

- The safety population includes all participants who receive ClariFix treatment
- The efficacy population includes all participants who receive ClariFix treatment and have least 1 valid follow-up assessment

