**Figure 2. ClariFix™ Device**

## 2.5 RISK/BENEFIT ASSESSMENT

### 2.5.1 KNOWN POTENTIAL RISKS

The study cryotherapy procedure involves transnasal placement of the ClariFix device under endoscopic visualization and use of local anesthesia. In order to minimize risks associated with the study, the procedure will be performed by practicing otolaryngologists experienced in transnasal procedures. Further, subjects with known allergies to local anesthetic agents shall be excluded from participation in the study.

While nasal endoscopy is generally known to be safe, anticipated risks may include, but are not limited to:

- Temporary pain, discomfort or irritation
- Bleeding
- Cerebrospinal fluid (CSF) leak

Similarly, while generally known to be safe, submucosal placement of a needle and delivery of local anesthesia may be additionally associated with the following risks, not limited to:

- Minor bleeding
- Pain with injection
- Facial numbness or tingling
- Sedation
- Tachycardia, nervousness, anxiety
- Lightheadedness, dizziness, confusion,
- Muscular twitching, tremors
- Infection
- Allergic reaction
- Lidocaine or Tetracaine toxicity with overdose
- Visual disturbance
- Vomiting
- Headache
- Tinnitus
- Seizures
- Hypotension, bradycardia
- Unconsciousness
- Respiratory arrest
- Cardiac arrest

While generally considered safe, cryotherapy has known potential risks including, but not limited to:

- Postoperative bleeding
- Epistaxis
- Nasal obstruction
- Nasal crusting
- Ear blockage

In addition, the specific nature of cryosurgery using the ClariFix Device results in a known potential for adverse events related to the cold application. Potential risks and complications are outlined in the IFU (See Appendix I).

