## 6 STUDY TREATMENT

### 6.1 STUDY TREATMENT ADMINISTRATION

All subjects will receive bilateral cryoablation treatment with the ClariFix device per Instructions for Use (IFU) (See Appendix I).

Each side of the nasal cavity will be treated in two locations (see Figure 3): (a) middle meatus and (b) inferior meatus. Each location will receive approximately thirty (30) seconds of cryoablation treatment.

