## 7 STUDY INTERVENTION DISCONTINUATION AND PARTICIPANT DISCONTINUATION/WITHDRAWAL

### 7.1 PARTICIPANT DISCONTINUATION/WITHDRAWAL FROM THE STUDY

Participants are free to withdraw from participation in the study at any time upon request.

An investigator may discontinue or withdraw a participant from the study for the following reasons:

- Significant study non-compliance
- If any clinical adverse event (AE), laboratory abnormality, or other medical condition or situation occurs such that continued participation in the study would not be in the best interest of the participant
- If the participant meets an exclusion criterion (either newly developed or not previously recognized) that precludes further study participation

The reason for participant discontinuation or withdrawal from the study will be recorded on the Study Exit Case Report Form (CRF). Subjects who sign the informed consent form but do not receive the study treatment may be replaced. Subjects who sign the informed consent form and receive the study treatment, and subsequently withdraw, or are withdrawn or discontinued from the study, may be replaced at the discretion of the Sponsor.

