## 9.3 POPULATIONS FOR ANALYSES

There are two key populations for analyses:

- The Safety Population is comprised of those subjects who received treatment by the ClariFix device
- The Efficacy Population is comprised of those subjects in the Safety Population who also had at least one valid follow-up assessment.

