8.1 Safety analysis cohort

Safety analysis cohort is all participants treated with the ClariFix device.

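### The safety set requires ClariFix treatment, so a procedure-related SAE followed by abandonment before any freeze would be left out of the primary incidence

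*SAP*

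**What the plan says.** Three places define who counts for safety, and they agree.

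- SAP 4.3: "The safety population includes all participants who receive ClariFix treatment".
- SAP 8.1: "Safety analysis cohort is all participants treated with the ClariFix device".
- Protocol 9.3: "The Safety Population is comprised of those subjects who received treatment by the ClariFix device".

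The only other analysis set, for efficacy, also requires treatment. Neither document has a set of enrolled participants or of attempted procedures.

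The primary endpoint (Protocol 1.1 and 3; SAP 3.1.1) is the incidence of procedure-related SAEs and/or SADEs. Protocol 2.5.1 describes the procedure broadly: "The study cryotherapy procedure involves transnasal placement of the ClariFix device under endoscopic visualization and use of local anesthesia". It adds that "submucosal placement of a needle and delivery of local anesthesia may be additionally associated with the following risks", and the list that follows includes seizures, respiratory arrest and cardiac arrest. Treatment itself is described as freezing: "Each location will receive approximately thirty (30) seconds of cryoablation treatment" (Protocol 6.1).

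On replacement, Protocol 7.1 says: "Subjects who sign the informed consent form but do not receive the study treatment may be replaced". SAP 3.1.3 sets the target at 30 treated participants.

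**The concern.** The endpoint follows the procedure, while the analysis set follows the freeze. The procedure starts earlier, with anaesthesia and placement, and the protocol itself names serious risks of those steps. A participant seriously harmed at that stage, whose procedure then stops before any cryoablation, meets the endpoint but belongs to neither analysis set.

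The primary result is a small count with no hypothesis attached (SAP 3.1.2), so one event decides whether the report says none or one. Any error from this rule can only lower the count, because the participants it leaves out are those whose procedure stopped early.

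**Working it through.** The plan has no figure to reproduce. The sample of 30 is a convenience sample with no power calculation, and no confidence interval is planned for the primary endpoint. The check compares definitions, and a short illustration follows.

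**Step 1. Set the provisions side by side** for a participant with a procedure-related SAE after anaesthesia and no freeze.

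| Place | Content | Reaches this participant? |
|---|---|---|
| SAP 3.1.1 | Primary endpoint: procedure-related SAEs and/or SADEs | Yes |
| Protocol 2.5.1 | Procedure includes anaesthesia and placement | Yes |
| Protocol 9.3; SAP 4.3, 8.1 | Safety set: treated only | No |
| Protocol 8.1.3 | AE assessment opens at Visit 3 | Yes |
| Protocol 8.4 | All SAEs collected | Yes |
| Protocol 8.4.1 | AE defined for subjects who receive device treatment | No |
| Protocol 8.4.6 | Recording window opens at device treatment | No |
| Protocol 9.4.4 | Incidence counted from time of treatment | No |
| Protocol 1.3, footnote a | Collection from the treatment timepoint; earlier AEs may go to medical history | Unclear |
| SAP 4.1, 5.1 | Listing of discontinuations; exit form for all participants | Yes |
| SAP 8.2.2 | SAEs listed by participant, no set named | Probably, but it sits under the treated cohort of 8.1 |

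The provisions for collection and listing mostly reach the participant. None of them brings the participant into the set on which the primary incidence is calculated.

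**Step 2. Find who is excluded.**

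- Anaesthesia given, device never used: outside the set on any reading.
- Device inserted, no freeze: outside on the natural reading of Protocol 6.1 and 8.1.3. This is arguable, because neither document defines what receiving treatment means.
- At least one freeze delivered at any site: inside the set. This includes a procedure stopped partway and one that reached the middle but not the inferior meatus. If the SAE came before that freeze, whether it counts depends on which start point applies: Visit 3 (8.1.3) or treatment (8.4.1, 8.4.6, 9.4.4).

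**Step 3. Illustrate the size.** The number of events is assumed and comes from neither document. Suppose one participant has a procedure-related SAE before any freeze, is not treated and is replaced. The other 30 have none.

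The exact (Clopper-Pearson) two-sided 95% limits for x events in n are:

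- upper limit = 0.975 quantile of Beta(x+1, n−x), which for x = 0 equals 1 − 0.025^(1/n);
- lower limit = 0.025 quantile of Beta(x, n−x+1), which for x = 1 equals 1 − 0.975^(1/n).

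For 0/30 the upper limit is 1 − 0.025^(1/30) = 1 − 0.8843 = 11.6%.

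| Scenario | As written | All started procedures |
|---|---|---|
| One event, replaced | 0/30 = 0% (0 to 11.6%) | 1/31 = 3.2% (0.1 to 16.7%) |
| One event, not replaced | 0/29 = 0% (0 to 11.9%) | 1/30 = 3.3% (0.1 to 17.2%) |
| Two events, both replaced | 0/30 = 0% (0 to 11.6%) | 2/32 = 6.3% (0.8 to 20.8%) |

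**The case against.** The strongest reply is that such a case would be visible. AE assessment opens at Visit 3, all SAEs are collected, and the sponsor must be told within 24 hours (Protocol 8.4.7). Participants are enrolled at baseline, so one whose procedure is abandoned at Visit 3 is an enrolled discontinuation with an exit form and a listed reason, not a screen failure. This stands. A reader might infer that the plan hides failed attempts, or that replacement erases them. The documents do not support either inference: Protocol 7.1 allows replacement but does not say that records or events are discarded. The loss is from the primary incidence, and a listing does not restore a numerator or a denominator.

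A reader might also infer that every SAE before the first freeze drops out. That is too broad. The set rule excludes a participant only if no freeze is ever delivered.

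The objective is the safety of treatment at the inferior meatus, and an anaesthetic event without cryoablation says little about that. This is a fair reason to keep a treated-only rate. It does not settle the primary endpoint, which the documents word in terms of the procedure.

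Finally, the event is unlikely. The pilot reports bilateral completion in 27 of 27 subjects, and the later 100-subject study describes all enrolled subjects as treated. Neither report mentions an abandoned procedure, though neither gives a count of procedures started and abandoned. A downward bias is therefore a possibility under the rule, not something the documents show will occur.

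**Conclusion.** The point holds in a narrow form. If a participant has a procedure-related SAE and the procedure is abandoned before any freeze, following the written rule leaves that participant out of both numerator and denominator of the primary incidence, and no other provision puts the participant back.

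This rests on reading receipt of ClariFix treatment as at least one freeze. That reading is secure where only anaesthesia was given and arguable where the device was inserted without freezing. The contrast of 0/30 with 1/31 also assumes one event, replacement, and 30 other participants without an event.

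The probability is low, with zero or one participant a reasonable expectation. No test or planned interval depends on the result; what changes is whether the headline safety count is none or one. It is a cheap improvement.

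**What to change.** 1. In Protocol 9.3 and SAP 4.3 and 8.1, define the safety set as all participants in whom the study procedure was started at Visit 3, meaning first anaesthetic administration or device insertion.
2. State in the same places that a participant who is replaced stays in the safety set, with any events counted.
3. Align the AE start point in Protocol 1.3 footnote a, 8.4.1, 8.4.6 and 9.4.4 with 8.1.3: Visit 3, from the start of the procedure. Without this step the participant would enter the denominator while the event could still go uncounted.
4. Report the treated-only rate alongside.

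The cost is three set definitions, four wording changes in the protocol and one extra line in the safety table. New data collection should not be needed: SAP 6 already collects anaesthesia medications and procedure times, provided those forms are also completed for an abandoned procedure. The downside is that the denominator may include a participant who had no freeze, which slightly dilutes freeze-specific rates. The treated-only rate covers that.

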4.4 Outcome variables

4.4.1 Efficacy outcome variables

The following outcome variables will be collected and analyzed as primary, secondary, or exploratory efficacy outcomes:

- Procedure pain scores (NPRS): during the procedure and immediately post procedure
- rTNSS: collected at baseline and at 30-day and 90-day follow-up visits
- Quantitative nasal endoscopy scores: collected at baseline, procedure, and at 30-day and 90-day follow-up visits
- NOSE: collected at baseline and at 30-day and 90-day follow-up visits
- SNOT-22: collected at baseline and at 30-day and 90-day follow-up visits
- Nasal symptom VAS: collected at baseline and at 30-day and 90-day follow-up visits
- Mini RQLQ: collected at baseline and at 30-day and 90-day follow-up visits

4.4.2 Safety outcome variables

- Serious adverse events and serious adverse device effects
- Nonserious adverse events and adverse device effects

4.4.3 Other variables

Other variables for analysis include procedure characteristics (See **Section 6**) and physician ease of device use.

5 Demographics and Baseline Characteristics

Demographics will include:

- Date of birth (age will be auto-calculated from the date of birth)
- Sex (male, female, not specified)
- Race (American Indian or Alaskan native, Asian, black or African American, native Hawaiian or other Pacific Islander, white or Caucasian, and other, specify)
- Ethnicity (Hispanic or Latino/not Hispanic or Latino)

Medical history will include allergy status, duration of rhinitis, and previous response to treatment with ipratropium bromide (IB). History of other medical conditions will include sinusitis, chronic nosebleeds/epistaxis, eye symptoms, facial pain, temporomandibular joint disorders (TMJ), hearing complaints, migraines, asthma, and gastroesophageal reflux disorder (GERD).

Previous ENT surgical procedures (eg, turbinate reduction, sinus surgery, septoplasty) will be noted. Concomitant medications will be collected.

Other baseline measures include the quantitative nasal endoscopy examination and PRO questionnaires (rTNSS, NOSE, SNOT-22, VAS, and mini RQLQ).

5.1 Participant disposition

A Study Exit form will be completed for all participants upon completion of all planned study requirements or early exit, as applicable. For those participants exiting before completing all the study requirements, the reason for the study exit will be noted. For follow-up visit compliance, once a participant has exited the study, they are no longer included in the denominator for future visits.

6 Procedure Data

Procedure data will include the date of treatment, treating physician, anesthesia medications and doses, and procedure times. For each treatment location (right and left, inferior and middle meatus), the freeze duration (seconds) and number of freezes will be collected. Up to 2 treatments are permitted per location. The number of devices used (and lot numbers) will be collected as will any reports of device malfunction.

7 Efficacy Outcomes

7.1 Efficacy analysis cohort

The efficacy analysis cohort is all participants treated with the ClariFix device who also have at least 1 valid follow-up assessment.

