### 8.3 SAFETY AND OTHER ASSESSMENTS

---

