### 8.3.2 PAIN NUMERIC RATING SCALE

A pain numeric rating scale (NRS) for pain function best for the patient's subjective feeling of the intensity of pain right now—present pain intensity. The NRS utilizes an 11-point scale of zero to 10. Subjects verbally report pain on the scale of 0 to 10 with zero representing “no pain” and 10 representing “worst pain imaginable”.

Pain and/or discomfort during the Treatment Visit (Visit 3) will be collected for each individual freeze treatment location (left middle meatus, left inferior meatus, right middle meatus, and Right Inferior Meatus), and any post-treatment pain and/or discomfort reported immediately following the treatment.

---

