7.2 Efficacy outcomes

7.2.1 Procedure pain/discomfort

A secondary endpoint is the tolerability of the procedure. Current intensity of pain/discomfort is verbally provided by the participant during the procedure for each treatment location and overall immediately post procedure. Pain/discomfort is assessed using the 11-point NPRS where 0 indicates no pain/discomfort and 10 indicates the worst pain/discomfort imaginable.¹

The count and percentage of participants indicating pain and the mean \pm SD pain score will be calculated. The termination of any procedure due to pain will also be noted.

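### Procedure pain is scored only on Day 0, but the SAP places it under a cohort that requires a later follow-up assessment

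*SAP*

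**What the plan says.** SAP 3.1.1 names tolerability, measured by the participant's verbal NPRS rating, as a secondary endpoint.

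The SAP then treats it as efficacy in two places. The first item in 4.4.1 (Efficacy outcome variables) is "Procedure pain scores (NPRS): during the procedure and immediately post procedure", and 7.2.1 reports it under the heading for efficacy outcomes. The planned summary there is "The count and percentage of participants indicating pain" plus the mean and SD. The same subsection adds: "The termination of any procedure due to pain will also be noted".

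The one cohort stated for Section 7 is in 7.1: "The efficacy analysis cohort is all participants treated with the ClariFix device who also have at least 1 valid follow-up assessment". Section 7.2.1 names no cohort of its own. The safety variables in 4.4.2 and the safety outcomes in Section 8 cover adverse events only; NPRS is in neither. An all-treated set is already defined in SAP 4.3: "The safety population includes all participants who receive ClariFix treatment".

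In the protocol, the Schedule of Activities and 8.1.3 collect the pain score at Visit 3 (Day 0) and at no other visit. Section 8.3.2 says that pain at that visit "will be collected for each individual freeze treatment location", with any pain immediately afterwards recorded too. That section sits under 8.3, headed "SAFETY AND OTHER ASSESSMENTS".

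**The concern.** Every treated participant can give a pain score on Day 0, whether or not they come back. Making the summary depend on a later assessment removes data already in hand. The exclusion could also be related to the outcome: someone who found the procedure very painful, or whose procedure was stopped for pain, may be less likely to return. That link is plausible, but the documents contain no data on it.

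The study exists to assess safety and tolerability when an inferior meatus treatment is added, and the per-location scores are among the few planned data on tolerating it. SAP 10.4 plans no sensitivity or missing-data analysis that would bring such a participant back in. Protocol 7.1 lets the sponsor replace treated participants who withdraw, so a dropped participant need not show up as a shortfall from 30.

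**Working it through.** The plan gives no figure to reproduce: N = 30 is a convenience sample (SAP 3.1.3) and pain is described, not tested. The check has three parts.

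**1. Which set applies to pain**

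- Variable list: SAP 4.4.1 has NPRS under efficacy; 4.4.2 (safety) does not have it.
- Results section: 7.2.1, directly below the 7.1 cohort. Section 8, which uses all treated, does not mention it.
- Override: none in 7.2.1.

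A programmer following the SAP would therefore apply the 7.1 cohort.

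**2. How many could be dropped**

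Inputs from Protocol 2.3: 27 of 27 pilot subjects and 100 of 100 subjects in the post-market study completed 30-day follow-up, so 0 of 127 were lost before Day 30. With no events in n subjects, the one-sided 95% upper limit is 1 - 0.05^(1/n).

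- Both studies: 1 - 0.05^(1/127) = 0.0233. Expected in 30: 30 × 0.0233 = 0.70.
- Post-market study alone: 1 - 0.05^(1/100) = 0.0295. Expected in 30: 30 × 0.0295 = 0.89.
- Chance of at least 1 of 30 at the pooled limit: 1 - (1 - 0.0233)^30 = 0.507.

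The observed rate is zero, so 51% describes the upper limit and is not a forecast. For other assumed loss rates the same formula gives 26% at 1%, 79% at 5% and 96% at 10%.

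**3. What a dropped participant does to the summary**

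Let m be the mean NPRS of those kept (assumed; the documents give no value), x the score of each dropped participant (0 to 10), and k the number dropped. The all-treated mean minus the reported mean is k(x - m)/30.

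| Assumed m | k = 1, x from 0 to 10 | k = 2, x from 0 to 10 |
|---|---|---|
| 1 | -0.03 to +0.30 | -0.07 to +0.60 |
| 3 | -0.10 to +0.23 | -0.20 to +0.47 |
| 5 | -0.17 to +0.17 | -0.33 to +0.33 |
| 7 | -0.23 to +0.10 | -0.47 to +0.20 |

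For example, with m = 3 and one dropped score of 10: (29 × 3 + 10)/30 = 3.23, against 3.00 reported.

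The percentage with pain shifts by at most k/30: 1/30 = 3.3 points for one dropped, 2/30 = 6.7 points for two. A single procedure stopped for pain in a non-returner would be 1/30 (3.3%) in all treated, but 0/29 in the 7.1 cohort.

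**The case against.** The strongest reply is that 7.2.1 states no cohort, so the exclusion is a reading of section placement and the defect is only an unstated analysis set. The sentence on terminations speaks of any procedure, which reads naturally as all of them, and Protocol 9.4.1 bases analyses on available data. It is fair that the cohort is inferred, and the inference is weakest for terminations. But the SAP gives pain no other set, and an available-data rule does not override a population definition.

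The protocol's placement of pain in 8.3 is weak support. That section is mixed: it also holds the assessment of congestion and turbinate hypertrophy, which Protocol 9.4.3 analyses with the efficacy endpoints. This objection stands, and the conclusion does not rely on that placement.

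The reach may also be narrower than it looks. The SAP does not define a valid follow-up assessment. SAP 4.1 limits Day 7 to adverse event and medication review, while Protocol 9.4.2 lists 7-Day among the efficacy table timepoints. If Day 7 counts, only someone with no follow-up visit at all is dropped; if it does not, someone seen only at Day 7 goes too.

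Finally, much would still be reported. Under Protocol 8.1.3, post-procedure pain also goes on an adverse event form. Adverse events are analysed in all treated (SAP 8.1), adverse device effects are listed by participant (SAP 8.2.2), and early discontinuations are listed with reasons (SAP 4.1). So a painful event would remain visible. What is lost is the NPRS score, including the per-location scores that the tolerability endpoint uses.

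**Conclusion.** The concern holds, at minor severity. Followed as written, the SAP makes a Day 0 secondary endpoint depend on later attendance. On the retention in the two prior studies the likely number affected is zero, and at the upper limit about 0.7 of 30. One exclusion would move the percentage by at most 3.3 points and the mean by no more than 0.30 in either direction over assumed means of 1 to 7. The direction is unknown. No hypothesis test is planned on pain, so no p-value is affected.

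This rests on three assumptions: that the 7.1 cohort governs 7.2.1; that earlier retention carries over to this study, although the 100-subject study treated the middle meatus only; and the illustrative mean scores. Confidence is medium, mainly because of the first.

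**What to change.** State in SAP 7.2.1 that NPRS scores and procedures terminated due to pain are summarised in the safety population, using the scores available at each treatment location and post procedure, with n shown for each. A stopped procedure may have no score at an untreated location, so n can differ between locations. Add a matching sentence in 4.4.1 and in 7.1 so that the three places agree. The 7.1 cohort stays as it is for the other outcomes.

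The cost is one sentence in each of the three sections, with no new data or analysis. The n in the pain table may then differ from the other Section 7 tables and needs a footnote.
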